#### 1.4. Serious adverse (drug) reaction (SADR)

Serious adverse reaction is an adverse reaction, which results in death, is life-threatening, requires in-patient hospitalisation or prolongation of existing hospitalisation, results in persistent or significant disability or incapacity, or is a congenital anomaly/birth defect.

“Life threatening” in this context refers to a reaction in which the patient was at risk of death at the time of the reaction; it does not refer to a reaction that hypothetically might have caused death if more severe.

Medical and scientific judgement should be exercised in deciding whether other situations should be considered serious reactions, such as important medical events that might not be immediately life threatening or result in death or hospitalisation but might jeopardise the patient or might require intervention to prevent one of the other outcomes listed above.

Examples of such events are intensive treatment in an emergency room or at home for allergic bronchospasm, blood dyscrasias or convulsions that do not result in hospitalisation or development of dependency or abuse.

Any suspected transmission via a medicinal product of an infectious agent is also considered a serious adverse reaction.

## 2. Responsibilities

### 2.1. Events to be reported

All available information about the following reported events occurring during the study will be recorded:

- All serious adverse drug reactions related to a Servier drug used for the disease/condition subject of the present study
- All non-serious adverse drug reactions related to a Servier drug used for the disease/condition subject of the present study
- All reports about special situations (see 1.1)
- All adverse events

### 2.2. Responsibilities of the treating physician

In prospective studies, at medical visits, the treating physician will ask the patient participating in the study to indicate whether or not an adverse event (serious or not) has occurred.

The treating physician has to assess the causal relationship between an adverse event and a drug intake, as well as the seriousness criteria and later on the outcome of the event.

In case of Adverse Events, Adverse Drug Reactions or special situations that occurs during the study (both serious and non-serious), the treating physician must complete the **“Adverse event / Adverse drug reaction / Special Situation Reporting Form” (Appendix 1)** without waiting for the clinical outcome or the results of additional investigations.

If the event is serious, it will be notified immediately (same or next working day at the latest) to Servier company in Russia via e-mail to address [[contact]](mailto:[contact]) or by fax to number [name]. The anonymized copies of all the available and relevant laboratory findings, hospitalisation reports or other investigation results performed in connection with the adverse event should be attached to the form.

All other events should be reported by a treating physician within 2 working days.

The same rules apply for the transferring of additional information about the event.

The treating physician must ensure the appropriate follow-up of the patient depending on the nature of event, until it resolves. The treating physician will continue to notify follow up data according to timeframes defined above.

If a treating physician does not follow-up a patient anymore (i.e. in case of hospitalisation followed by the treatment by specialist or the participant's general practitioner,...), he/she will do every effort to contact the specialist or department in charge of follow-up of the patient, so as to have additional information and report it to Servier company in Russia.

### 2.3. Responsibilities of the Sponsor

Independently of the regulatory obligations of the treating physician, the sponsor must report the pharmacovigilance data to the appropriate authorities in accordance with the Good Vigilance Practice and local regulations.

Cases are closed when an adverse event has recovered or patient's condition was stabilised and the report is deemed sufficiently detailed for adequate medical analysis of the case.

# Statistical parameters

## 1.1 Statistical design and analysis

Statistical analysis will be performed using validated statistical software that will be selected and approved by the Sponsor no later than the date of database lock. Examples of validated statistical software include, but not limited to, licensed versions of SAS (9.4 or higher), SPSS (21 or higher), NCSS (2019 or later), etc. Adverse events will be coded using Medical dictionary for regulatory affairs (MedDRA), MedDRA version (24.0 or higher) will be chosen at the time of data base lock.

## 1.2 Analysis populations

Full analysis set (FAS) will be the main analysis population for all statistical descriptions and testing. This analysis set will include all study subjects that were included into the study without major deviation from entry (inclusion and exclusion) criteria and successfully accomplished it (data and images met inclusion/ no inclusion and exclusion criteria and therefore are taken into analysis by the app).

No imputation methods will be applied for any data that is missing from the FAS due to non-comparative nature of the study.

FAS will be used for all additional sensitivity analyses, if such analyses are required.

## 1.3 Descriptive statistics

Continuous (quantitative) data will be presented as number of valid observations, arithmetic mean, standard deviation, median, interquartile range (presented as 1st and 3rd quartiles), minimum and maximum.

Categorical (quantitative) data will be presented as number of valid observations, number of observations falling into each category (absolute frequency), relative frequency (presented as % values).

95% confidence intervals will be presented for all types of data to measure the precision of sample estimate. Confidence intervals will be based on t-distribution for quantitative data, and on the binomial distribution (exact Clopper-Pearson method or Agresti-Coull method) for qualitative data.

Concurrent conditions and adverse events will be classified using the current version (at the time of database lock) of MedDRA (Medical Dictionary for Regulatory Activities). Concomitant medications will be classified using the most up-to-date version (at the time of database lock) of ATC (anatomical, therapeutical and chemical) classification system.

## 1.4 Baseline information

Due to non-comparative nature of the study, baseline data will be presented descriptively, without any statistical testing of comparisons (as detailed in section 1.3 above). Yet, as the study will test the performance for C 1 and C 2 classes separately, baseline data will be presented by C class on top of general sample data.

## 1.5 Primary endpoints

The following primary parameters will be assessed in this study:

1. Sensitivity and specificity of the AIVARIX tool in detecting C 1 class of CVD.
2. Sensitivity and specificity of the AIVARIX tool in detecting C 2 class of CVD.

Calculation of all performance parameters will be based on the two-way table as follows (where “gold standard” stands for the current approach and “screening test” stands for AIVARIX-based approach; “positive” stands for signs

of C1 class of CVD or C2 class of CVD, “negative” stands for non-signs C1 class of CVD or non-C2 class of CVD, respectively):

Primary (operational) parameters of the AIVARIX method will be calculated as follows (presented as percentages):

$$Sensitivity = [a/(a+c)] \times 100$$

$$Specificity = [d/(b+d)] \times 100$$

95% exact binomial confidence intervals calculated using the Clopper-Pearson or Agresti-Coull method will be calculated for both sensitivity and specificity.

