## Aim of the program

The main goal of this study is to describe the AIVARIX app accuracy in detecting C1 and C2 classes by CEAP classification of chronic venous disease (CVD) in patients who are consulted by phlebologists on symptoms and signs suggestive to CVD.

Primary goal(s):

The primary goal of the study is to estimate Sensitivity (Sn) and Specificity (Sp) of the AI-based AIVARIX app in detecting C1 and C2 classes of CVD in patients who are seeking for professional advice from a phlebologist regarding symptoms and signs suggestive to CVD.

- Sensitivity is defined as the ratio of the number of positive cases of detection of signs of C1 or C2 CVD, identified using the AIVARIX tool, to the total number of truly positive cases of C1 or C2 CVD in the study population, confirmed by phlebologists using objective / instrumental examinations.
- Specificity is defined as a proportion of the number of negative cases of signs C1 or C2 classes of CVD identified by the AIVARIX tool divided to overall truly negative cases of C1 or C2 in the study population confirmed by phlebologists by means of objective/ instrumental examination.

Once Sn and Sp of the application is estimated, positive and negative likelihood ratios (LR) will be calculated.

Secondary goal(s):

Secondary objectives are to calculate the positive and negative predictive values (PPV and NPV, respectively) of AIVARIX in detecting signs of C1 and C2 classes of chronic venous disease.

PPV is defined as the proportion of true positive cases of class C1 or C2 CVD detected using AIVARIX as a proportion of the number of true positive and false positive cases of class C 1 or C 2 identified using the AIVARIX application and confirmed by phlebologists.

The NPV is defined as the ratio of the number of true negative cases of C 1 or C 2 CVD detected using AIVARIX to the true negative and false negative cases of C 1 or C 2 CVD detected using AIVARIX and confirmed by phlebologists.

Primary Variables:

- Sensitivity and specificity of the AIVARIX app in detecting C 1 class of CVD.
- Sensitivity and specificity of the AIVARIX app in detecting C 2 class of CVD.

Secondary Variables

- PPV, NPV, LR+ and LR- of the AIVARIX app in detecting C 1 class of CVD
- PPV, NPV, LR+ and LR- of the AIVARIX app in detecting C 2 class of CVD

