## Methodology

This is a cross sectional multicenter prospective observational study. It will include patients seeking phlebologist's consultation with any signs and symptoms suggestive to CVD including but not limited to C1 and C2 classes as well as patients without CVD who have other skin pathologic conditions of lower extremities that require differential diagnosis with CVD. Twenty-one phlebologists consulting in outpatient clinics across the country will be participating in the study.

The total number of patients as well as the number of patients with CVD C1 and C2 classes, the number of patients with other classes of CVD and the number of patients with other skin pathologic conditions of lower extremities are estimated given data on prevalence of CVD classes in general population available for Russia and other countries. This estimation is described in the "Sample size calculation and justification" paragraph. According to the mentioned estimation a distribution of patients to be enrolled in the study by each participating phlebologist should be as following:

- 20 subjects overall of whom:
  - 6 patients with CVD C1 class
  - 4 patients with CVD C2 class;
  - 2 patients with CVD with classes other than C1-C2 (C4-C6);
  - 8 patients with either C0s CVD or with skin pathologic conditions of lower extremities other than CVD;

Patients will be screened by a phlebologist and if meet inclusion/ non-inclusion criteria and provide written consent to participate in the study will be included in the study. Phlebologist will evaluate patients' status locales in accordance to routine clinical practice to objectively confirm or exclude presence of CVD and to define a class of the disease if present. Presence of CVD and associated class by C will be confirmed based on results of diagnostic methods used in routine clinical practice (presumably with use of objective examination, anamnesis morbi and ultrasonography of veins of lower extremities and/ or by venography of lower extremities, if necessary).

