Once the clinical evaluation is made, investigating physician will take one photo of the locus with spider veins in patients present with C1 class, or with varicose veins for patients present with C2, or locus with either no signs of pathology or with pathologic condition of the skin of lower extremities other than CVD in accordance to the distribution split described herein above, and then will upload the picture to the cloud storage. Phlebologists participating in the study will also record results of the clinical evaluation for each enrolled patient in the eCRF with imputing the information on presence or absence of CVD with obligatory indication of class by C as well as presence or absence of other skin pathologic condition(s) of lower limbs that required consultation and differentiation by phlebologist. If a patient has CVD simultaneously present with signs of C1 and C2 as well as with other classes of CVD a phlebologist will have to decide which locus of pathology to picture in accordance to the given distribution of patients to be enrolled. In case a patient has no CVD but any other skin pathologic condition of lower extremities of different nature a phlebologist will take one photo of the locus with a corresponding pathologic sign(s) and then upload it to the cloud. In any cases investigating phlebologist will record information on presence or absence of CVD indicating its class or other pathologic condition in the eCRF.

Each uploaded photo must be deindividualized and should have a unique ID code assigned to each patient.

In order to fulfill minimum requirements for technical characteristics of smartphones/ pictures to be taken, following criteria are to be satisfied:

- Smartphone is to be manufactured in 2015 or later but not earlier.
- Area of the interest is to occupy not less than 30% of the picture. To fulfill this requirement a smartphone has to be positioned so that the distance from the skin area of interest to smartphone's camera is in range of 30-50 cm.
- Plain background (a picture is to be taken at the background of plain/ monochromic wall/ surface without any additional subjects in focus including additional parts of the body, furniture or people, etc.).
- Smartphone is to be positioned in parallel to the skin area of interest.

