Once required number of patients is achieved and all images uploaded to the cloud storage they will be downloaded and analyzed by the AIVARIX application. For each photo the app will make a conclusion regarding possible presence or absence of CVD C1 or C2 that will be then compared with the conclusion made by an investigating physician. Eventually, based on obtained results, the Sensitivity and Specificity of the app will be established.

Additionally, to validate the tool with established Sensitivity and Specificity, a concordance between the confirmed diagnosis and signs of the app will be assessed. The Cohen's Kappa and Percentage agreement will be calculated for this purpose.

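### The primary specificity intervals ignore clustering by phlebologist and so are not calibrated for inference beyond the 21 participants; the size and direction of the error rest on figures the plan does not give

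*Combined protocol and SAP*

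**What the plan says.** Section 1.5 takes sensitivity and specificity for C1 and for C2 from a pooled two-way table and plans that "95% exact binomial confidence intervals calculated using the Clopper-Pearson or Agresti-Coull method will be calculated for both sensitivity and specificity". Both methods assume independent patients.

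The Methodology section describes how the data arise. "Twenty-one phlebologists consulting in outpatient clinics across the country will be participating in the study", and the "distribution of patients to be enrolled in the study by each participating phlebologist should be as following": 20 patients each, namely 6 C1, 4 C2, 2 C4-C6, and 8 with C0s or a non-CVD skin condition. The same phlebologist examines the patient, takes the one photo and records the class. On the reference side, "Presence of CVD and associated class by C will be confirmed based on results of diagnostic methods used in routine clinical practice". Where classes coexist, "a phlebologist will have to decide which locus of pathology to picture in accordance to the given distribution of patients to be enrolled". On equipment, "Smartphone is to be manufactured in 2015 or later but not earlier". The app then reaches a conclusion for each photo "that will be then compared with the conclusion made by an investigating physician".

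The Aim section sets the target as accuracy "in patients who are consulted by phlebologists on symptoms and signs suggestive to CVD", with no restriction to the participating phlebologists.

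Site appears in the analysis only in Section 1.14, as by-site description plus a nominal chi-square test if the endpoints look substantially different. Neither step alters the primary interval. Section 1.11 contains no design effect.

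**The concern.** Within a phlebologist, the image the app reads and the diagnosis it is scored against have one source. Photo technique, choice of locus, and habits in assigning the class can all shift specificity from one phlebologist to the next. A one-sample binomial interval has no term for such variation. If the result is to describe patients of phlebologists generally, the 21 phlebologists are a sample, and the interval should reflect that.

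Specificity is more exposed than sensitivity because the clusters of negatives are larger: 14 or 16 per phlebologist, against 6 or 4 positives. Specificity is a primary result, and Section 1.11 calls 60% unacceptable. A misstated lower limit would therefore affect how the app is judged. LR+ and LR- inherit the variance of specificity.

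**Working it through.** **Inputs.** From Methodology: 21 phlebologists and the quota 6/4/2/8. From Section 1.5: a negative is any non-C1 patient (C1 analysis) or any non-C2 patient (C2 analysis). From Section 1.11: 60% null specificity, 70% target, 80% power, 10% loss. Assumed, because the documents give no value: ICC of 0 to 0.10, and class-specific specificities.

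**The plan's own sizes, under independence.** A two-sided 5% test of 60% against 70% gives 181 by the exact binomial (power 80.1%) and 186 by Agresti-Coull (82.0%). For sensitivity (60% against 80%) the sizes are 45 and 44. Then 2 x 186 = 372, and 372/0.9 = 413.3, so 414. These agree with Section 1.11.

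**Negatives per phlebologist.** C1: 4 + 2 + 8 = 14, and 21 x 14 = 294. C2: 6 + 2 + 8 = 16, and 21 x 16 = 336. After 10% loss, about 265 and 302. These are approximate, since 21 x 20 = 420 against 414 planned.

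**Design effect**, if specificity is the same in every class: DE = 1 + ICC x (n_w - 1). Here n_w is the size-weighted mean cluster size after random loss, 0.9 x 14 + 0.1 = 12.7 (C1) and 0.9 x 16 + 0.1 = 14.5 (C2).

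- ICC 0.02: DE = 1.23 and 1.27; effective negatives 214 and 238.
- ICC 0.05: DE = 1.59 and 1.68; effective negatives 167 and 181.
- The effective number falls to the planned 186 at ICC 0.036 (C1) and 0.046 (C2).

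At 70% specificity the between-phlebologist SD is sqrt(ICC x 0.70 x 0.30): about 4.6, 6.5, 10 and 14.5 points at ICC 0.01, 0.02, 0.05 and 0.10.

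**Coverage, same specificity in every class.** Beta-binomial simulation, 20,000 datasets per scenario, 21 clusters, 10% loss, true specificity 70%. Repeat runs agree to within about one point.

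| Assumed ICC | Clopper-Pearson, C1 | Clopper-Pearson, C2 |
|---|---|---|
| 0.01 | 94.5% | 94.2% |
| 0.02 | 93.3% | 92.6% |
| 0.05 | 89.2% | 88.4% |
| 0.10 | 83.4% | 81.1% |

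**Coverage, specificity differing by class.** Because each class count is fixed, between-class differences add nothing to the sampling variance, but the binomial formula counts them. Example for C1 with specificity 35% in C2 patients and 84% in the rest:

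- Mean: (4 x 0.35 + 10 x 0.84)/14 = 0.70.
- Average variance per patient: (4 x 0.35 x 0.65 + 10 x 0.84 x 0.16)/14 = 0.161, against 0.70 x 0.30 = 0.210, a ratio of 0.77.

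This reduction offsets the clustering. With a logit-normal phlebologist effect of SD 0.3 (ICC about 0.02) or 0.5 (about 0.05), Clopper-Pearson covers:

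| Specificity by class | SD 0.3 | SD 0.5 |
|---|---|---|
| 45/80/80% (C1 and C2) | 94.8-94.9% | 91.1-92.2% |
| 35/84/84% (C1) | 96.3% | 94.3% |
| 35/91/91% (C2) | 97.8% | 96.0% |

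**Clustered interval.** A logit interval with variance clustered by phlebologist covered 94.8 to 95.6% across both kinds of scenario.

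**Other measures.**

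- Sensitivity at 80%: Clopper-Pearson covers 94.1% (C1) and 95.1% (C2) at ICC 0.05, and 91.3% and 94.0% at 0.10. The clustered interval does poorly near 100%: at true C2 sensitivity of 97% and ICC 0 it is undefined in 10.3% of datasets and covers 87.2%, against 98.9% for Clopper-Pearson.
- LR+ (log-scale Wald, sensitivity 80%, specificity 70%): 93.9, 92.5-92.9, 89.1 and 83.3-83.4% at ICC 0.01, 0.02, 0.05 and 0.10, against 95.0-95.4% with clustered variance. Section 1.6 does not name the scale, so the log scale is an assumption.
- LR- (log-scale Wald): 92.3% (C1) and 93.3% (C2) at ICC 0.05.
- Wald at ICC 0.05: PPV 97.3% (C1); NPV 94.6% (C1) and 94.9% (C2). No material shortfall.

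**The case against.** **The target may be narrower.** The Aim section defines both measures within the study population and describes the purpose as descriptive, and Section 1.3 presents intervals as the precision of a sample estimate. If the 21 phlebologists are treated as fixed, the binomial interval is not too narrow. This stands. The point applies only to the wider inference that the Aim section's target population invites.

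**There is no evidence of clustering.** One app reads every image centrally, and distance, framing, angle and background are prescribed. The documents contain no ICC, and at 0.01 the loss is negligible. This also stands, but it does not favour the binomial interval: the clustered one costs almost nothing when there is no variation.

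**The quotas may cancel the effect.** They may, as the mixed-class results show. A reader might infer that the planned intervals are simply too narrow. The documents do not support that, because it also depends on how specificity differs by class.

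**Sixty percent is not a pass mark.** A reader might also infer an inflated risk of a false claim of adequate specificity. At true specificity of 60% and similar classes, the Clopper-Pearson lower limit exceeds 60% in 5.1 to 5.9% of studies at ICC 0.05, against at most 2.5% nominal. With strong class differences averaging 60%, the rate is 2.5 to 2.7% at SD 0.3 and 4.2 to 4.5% at SD 0.5. But Section 1.11 uses 60% as the null for sizing, and Section 1.5 states no success rule.

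**Section 1.14 would show heterogeneity.** In part. Taking each phlebologist as a site, at 70% specificity the chi-square test reaches p < 0.05 in 18% (C1) and 21% (C2) of studies at ICC 0.02, and in 48% and 56% at 0.05. Either way, the reported interval stays the same.

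**Conclusion.** The point holds in conditional form. For inference to patients of phlebologists in general, the Section 1.5 interval for specificity ignores a feature of the design and is not calibrated. If specificity varies between phlebologists and is similar across classes, it is too narrow: slightly at ICC 0.02 (coverage about 93%) and materially at 0.05 and above (90% or less). If specificity differs strongly by class, it can be near nominal or too wide. The ICC and the class-specific specificities are assumptions throughout.

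It would go too far to call the study undersized. Section 1.11 asks for 186 negatives, about 265 and 302 are expected after loss, and clustering uses up that margin only above ICC 0.036 (C1) or 0.046 (C2). It would also go too far to treat sensitivity as equally affected: at the same ICC its loss is smaller, although equal ICC for the two measures is itself an assumption. The change is worth making because the clustered interval was calibrated in every scenario examined, whichever way the binomial interval erred.

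**What to change.** - **Section 1.5, specificity for C1 and C2.** For inference beyond the participating phlebologists, pre-specify a logit interval with variance clustered by phlebologist. With x_j correct among n_j negatives for phlebologist j, N negatives in all, pooled proportion p and K = 21: variance of p = K/(K-1) x sum of (x_j - n_j p)^2 / N^2; standard error of logit p = square root of that variance, divided by p(1-p); t on 20 df. Report the planned binomial interval beside it, and use the binomial interval alone if specificity is 0% or 100%.
- **Section 1.5, sensitivity.** Keep the binomial interval as primary and add the clustered interval as a sensitivity analysis in the FAS, which Section 1.2 allows.
- **Section 1.6.** Use clustered variance on the log scale for LR+ and LR-. Leave PPV and NPV as planned.
- **Data.** Carry a phlebologist identifier in the analysis dataset; the data collection sections do not list one.
- **Section 1.14** can stay.

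**Cost.** SAP wording, a few lines of code and the identifier. Specificity intervals average about 2% wider than Clopper-Pearson at ICC 0, 13 to 15% at 0.02 and 29 to 32% at 0.05. With true specificity 70%, the chance that the lower limit exceeds 60% changes as follows:

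| Assumed ICC | C1, binomial to clustered | C2, binomial to clustered |
|---|---|---|
| 0 | 91% to 89% | 95% to 93% |
| 0.02 | 90% to 82% | 93% to 86% |
| 0.05 | 87% to 71% | 89% to 74% |

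At ICC above 0, the higher binomial figures come from an interval that under-covers in these scenarios, so the difference is not all real power lost.
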